3.3.15 Qualitative Analysis

Data will be analysed as set out in phase I. As participants in this qualitative sample would also have responses to the quantitative data collected for the trial, this will allow for the possibility of taking a mixed-methods approach to data integration, in which the two forms of data can be used in a complementary way. For example, by using approaches such as 'triangulation protocol'¹ at a thematic level and 'mixed methods matrix'² at the level of individual cases, for data integration, greater insights will be gained from the process of data integration than would be obtained from using the two data types in isolation (52-53).

3.3.16 Economic analysis

The economic evaluation will take the form of within-trial cost-effectiveness analysis that will determine the incremental cost per unit of effectiveness measure for Social Stories compared with an attention control in children with autism. The choice of effectiveness measure will be informed by the choice of the primary outcome in the study. The evaluation will be carried out from the UK societal perspective, taking account of the use of health services, education services, and social and voluntary services over the study period. The cost of Social Stories intervention will be calculated using a bottom-up estimation of the time spent by professionals delivering the intervention, the cost of training and other resources used. Unit costs of health service use will be obtained from the UK national database of reference costs. The cost of social services will be calculated from the Unit Costs of Health and Social Care, produced by the Personal Social Services Research Unit (54), and the cost of other professional support will be estimated from relevant salary scales.

This pilot study will inform the choice of appropriate effectiveness measure for the economic analysis. Also it will identify the relevant resource use categories for the cost-effectiveness analysis, and evaluate the feasibility and challenges of measuring costs and outcomes in the target population.

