3.3.5 Trial Intervention

Schools will be randomised to one of two arms; the intervention group and the control group. Prior to the intervention teachers and parents of children in the intervention group will undertake training on Social Stories. We will run Social Stories training workshops informed by the earlier parts of the study. The Social Stories will be delivered in a way that is informed by the pre clinical theory and phase 1 of this study using the most promising mode of delivery. This will include who designs the Social Story with parent and child, how this is achieved, and how and when the Social Story is delivered with the child. For example this could include a teacher, support assistant, special educational needs coordinator and /or a parent and they will receive support as part of the study from the clinical researchers. The precise from of this support will be designed using findings from the pre clinical theory and phase 1 of this study.

We will check the construction of the Social Stories paying particular attention to construction guidelines as laid down by the original Social Stories model. We will also explore any other parameters, including construction, content and delivery that have been found to be related to outcome as part of the systematic review and user and expert panels. As part of this, for example, we will measure goals of the intervention, intervention agents, intervention setting, timings of the intervention, length of the intervention and number of stories per child. We will also assess characteristics such as the number and distribution of pictures and photographs, and the length and complexity of sentences, types of behaviours described and any allied interventions or support.

Whatever the precise methodology we will keep a record of all the design interactions and precise number, timings and locations of delivery. We will also record attrition, non

compliance and any distress. We will have a clear methodology of how to deal with any difficulties including child distress.

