In addition, a sample of 5 professionals and 5 parents/carers delivering the manualised intervention will be interviewed. The interview will be semi-structured, asking them to record: their experiences associated with delivering the intervention, in particular facilitators and barriers relating to its delivery within existing service models; their perceptions of whether the intervention does or doesn't work well, including their understanding of why; and any experiences they have with users receiving the intervention which highlight where it works well and less well, including perceptions of reasons for discontinuation with the intervention by any participant.

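### The economic evaluation is labelled societal but names no parent or carer time, although intervention-arm parents are trained, help design the stories and in some cases deliver them

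*Protocol*

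**What the plan says.** Protocol section 3.3.16 (Economic analysis) states the viewpoint and its content in one sentence: "The evaluation will be carried out from the UK societal perspective". The content is then given as four kinds of service use: health, education, social and voluntary. The intervention is costed bottom-up from the "time spent by professionals delivering the intervention", and the section adds "the cost of training and other resources used". The valuation sources are national reference costs, a published set of health and social care unit costs and, for the remainder, "the cost of other professional support will be estimated from relevant salary scales". Parents and carers do not appear in the section. Its closing paragraph adds that the pilot is meant to establish which resource categories matter and how feasible they are to measure.

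Other sections give parents a part in the intervention:

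- Section 3.3.5: "Prior to the intervention teachers and parents of children in the intervention group will undertake training on Social Stories". The story is designed with the parent and child, and a parent is among the people who might deliver it.
- Section 3.3.13: "a sample of 5 professionals and 5 parents/carers delivering the manualised intervention will be interviewed".
- Section 3.3.6: control parents are offered a Social Stories workshop, but only once the study has ended.
- Section 3.3.4: control children spend matched time on a comparable story, taken from a range picked by the expert panel.

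**The concern.** A societal perspective counts resources whoever bears them, so unpaid family time spent producing the intervention belongs in its cost. The items in section 3.3.16 describe a narrower viewpoint, that of public and voluntary services. An analyst who follows the listed items would report a service-perspective cost under a societal label.

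The gap matters because it is unlikely to be balanced between arms. Training and story design are asked of parents in the intervention arm only, so leaving them out would lower the incremental cost. The economic component exists mainly to inform a full trial: section 3.3.17 lists a justification of costs and cost-effectiveness among the outputs. A category that is not recorded in the feasibility study cannot be assessed for relevance or measurability, and the time cannot be recovered at analysis.

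**Working it through.** The protocol gives no hours, unit costs or cost totals on this point, so there is no figure to reproduce. The check sets the sections side by side and then illustrates the possible size on stated assumptions.

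**Step 1: which parent inputs differ between arms?**

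| Parent input | Intervention arm | Control arm during the trial | Cancels in the increment? |
|---|---|---|---|
| Training | Yes (3.3.5) | None; workshop only at the end (3.3.6) | No |
| Story design | Yes (3.3.5) | None indicated; expert panel selects the stories (3.3.4) | No |
| Reading the story | Some parents/carers (3.3.13); exact mode set by phase 1 (3.3.5) | Matched time; reader not stated (3.3.4) | Largely, if the same kind of person reads in both arms |

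For the first two rows, leaving parent time out lowers the incremental cost. The third row may contribute little.

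**Step 2: is any of this named in 3.3.16?** Delivery time is restricted to professionals. Training and other resources are costed, but the section does not say whether parents' attendance or writing time is included in either. The valuation sources are service unit costs and salary scales, and none of them prices unpaid time.

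**Step 3: hours, as an illustration.** Assumed per child: training 3-6 h, story design 1-2 h, reading 10-20 minutes a week. The 4-6 month delivery period in 3.3.8 is taken as 17-26 weeks. The 25 intervention children are from the Summary.

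- Training and design: 3 + 1 = 4 h to 6 + 2 = 8 h per child; × 25 = 100 to 200 h.
- Reading, if a parent does all of it: (10/60) × 17 = 2.8 h to (20/60) × 26 = 8.7 h per child.
- All three: 6.8 to 16.7 h per child; × 25 = about 171 to 417 h.

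Reading is 2.83/6.83 = 41% of the low total and 8.67/16.67 = 52% of the high total. About half of the larger figure is therefore the part that may cancel against the control arm.

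**Step 4: share of intervention-arm delivery-time cost left out, as an illustration.** Let f be parents' share of delivery hours and w the ratio of the parent to the professional unit cost; both are assumed. The share omitted is f·w / (f·w + 1 − f).

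| f | w = 0.25 | w = 0.5 | w = 1.0 |
|---|---|---|---|
| 0.10 | 3% | 5% | 10% |
| 0.25 | 8% | 14% | 25% |
| 0.50 | 20% | 33% | 50% |
| 0.75 | 43% | 60% | 75% |

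For example, f = 0.5 and w = 0.25 gives 0.125/0.625 = 20%. The share is zero if parents give no delivery hours or if their time is counted under other resources. This is a gross share within one arm. It overstates the effect on the increment wherever control reading is done by the same kind of person.

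**The case against.** The best defence is that the section is not closed. Its costing sentence goes beyond professionals' time to training and other resources, and parent time could be placed there. The resource categories are themselves something the pilot is to identify. The mode of delivery, and so the amount of parental work, waits on phase 1. Section 3.3.5 already plans a log of design interactions and deliveries, so much of the quantity data would exist. The rate for valuing unpaid time is a detail that an analysis plan could supply. The study is also a 50-child feasibility trial, not powered for differences and with no main outcome chosen.

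Much of this stands, and it rules out stronger readings. A reader might infer that the plan costs nothing but professionals' delivery time; the same sentence shows otherwise. A reader might infer that the intervention cost is certainly understated; that follows only if parent time is in fact left out. A reader might also take the equal interview samples in 3.3.13 to mean that parents deliver as much as professionals do. Those samples show that some parents deliver, but not how much.

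The mismatch itself is not answered. The perspective and the restriction of delivery time to professionals are both stated in the protocol, so they are not details held over for a later plan. A general reference to other resources, with no way to value unpaid time, gives an analyst little basis for including it. That the categories are still to be identified is a reason to record a foreseeable one from the start.

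**Conclusion.** The point holds as an inconsistency of scope: the stated perspective is wider than the costs named, and parents' time is the clearest omission because the protocol itself makes parents part of the intervention. If that time is left out, the incremental societal cost of the intervention is biased downwards, at least by training and story-design time. Reading time may add little because it is matched in the control arm.

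The size cannot be derived from the protocol. The 100-200 h for training and design, and the percentages by share of delivery, rest wholly on assumed inputs and show only that the amount need not be trivial. The larger total of about 171-417 h might be read as the amount wrongly valued at zero. The protocol does not support that reading: the total includes reading time that may cancel, and parent time is not expressly excluded.

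The issue touches neither participants nor the feasibility outcomes. It affects what the cost result means and what is passed to the full trial, and it should be settled before cost data are collected.

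**What to change.** In section 3.3.16, name parents' and carers' time for training, story design and delivery as an item in the bottom-up costing. State the rate at which it is valued, and report the incremental cost with and without it. In section 3.3.5, add two things to the log already planned: who delivered each session, and parent minutes. Keep the same record in the control arm where it applies, so that any cancelling of reading time is observed and not assumed.

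If the team does not want to cost family time, the alternative is to replace the societal label with one that names health, education, social and voluntary services.

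The first option costs a few extra record fields and one costing line. The second costs a change of wording, with a narrower claim for the result.

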4.0 Ethical arrangements

4.1 Anticipated Risks and Benefits

We do not anticipate that trial participants will be subject to any risks during this study. Social Stories are widely used and focus on positive social and situational coping, therefore are unlikely to cause participants harm. A possible ethical issue with the study is that the control group will not receive the Social Story intervention during the trial. We have combated this by holding a second free workshop for those parents within the control group at the end of the study on the use of Social Stories.

It is possible that parents may become distressed when talking about their child's ASD at the focus group. Their clinicians involved in the training are very experienced in dealing with distressed parents and are well placed to either provide support themselves or to refer to other support as necessary. Similarly should a child become distressed the teachers, clinicians and researchers will have discussed prior to the intervention any necessary actions, distractions, activities or support that will be employed in the event of distress. Again, staff are experienced in these situations.

4.2 Informing potential trial participants of possible benefits and known risks

Participants will be sent information leaflets by post. Information sheets will be provided for children and young people aged 4-10 and 11-15 aged and their parents. They will choose whether to make contact with a researcher by telephone. Therefore potential participants will always have a minimum of 24 hours to decide whether or not to take part. We will contact the participants by letter or telephone if any relevant information related to ASD or Social Stories becomes available during the study. All information leaflets and consent forms will be co developed by the research team and the PPI group to ensure acceptability amongst participants.

4.3 Obtaining informed consent from participants

If children or parents are interested in taking part in the study after they have read the information sheets they will be able to phone a researcher to make an appointment. They will meet the researcher where they have the opportunity to ask any questions they have relating to the research and consent to the study if they are happy to do so. Written consent will be obtained from parents and consent or assent from children and young people will be obtained where possible.

5.0 Service User Involvement

As part of the development of this detailed project description and in accordance with the INVOLVE guidelines (57) we have discussed the review and specific questions with a focus group made up of parents of children with ASD and teachers who use Social Stories to provide input on the study design. The group was asked to comment on various aspect of the proposed design of the study and the findings from the focus group were reported back to the research steering group and channelled into the development of the proposal.

The concept of a manualised Social Stories toolkit was received positively by the parents who made up this focus group. They highlighted the need for simplified, compact guidance on producing Social Stories which adhered to [name]'s model. In particular a common theme which ran through the focus group was the need for a clear, starting point from which to develop Social Stories once a challenging behaviour had been identified. They also felt that more guidance was necessary on the use of strategies for making sense of this behaviour and how to determine the focus of the Social Story, which may be different to working on the challenging behaviour as such. There was agreement between a number of parents involved in the focus group that the beneficial outcomes of using Social Stories were not limited to the specific context of the Story but were generalised to everyday situations. The focus group also drew attention to the role of collaboration in writing Social Stories between parents and teachers,

Some members from the focus group have been invited to attend the research steering group, where they will be able to inform the design, recruitment and dissemination phases of the research. We will conduct a second focus group of parents of children with ASD in the local area in phase 1 of the trial. Parents will be involved in the development of consent forms and information leaflets, advising on methods of recruitment and developing and implementing a dissemination strategy.

Parents will be recruited to the focus group from a variety of sources, such as the local ASD forum list and the ASCEND (Autism Spectrum Conditions - Enhancing Nurture and Development Group), a popular course provided in the York and Selby area for parents and carers of children with ASD (45). After phase 2 parents and teachers will be invited to offer comments in the design and acceptability of the research, as a main outcome measure, in order to inform a future large scale RCT of Social Stories versus treatment as usual for mainstream children with ASD exhibiting challenging behaviour.

The members of the research team have successfully used public-patient engagement strategies in their previous work, including funded systematic reviews. For example, applicant [name] used public-patient involvement as part of a HTA-funded review of screening methods for post-natal depression.

6.0 Research Governance

6.1 Data Protection/Confidentiality

Data is to be managed by the Research Assistant and only members of the research team will have access to personal data during the study. All participant information will be stored in accordance with the Data Protection Act 1998. Participant personal identifiable information will be stored in a locked filing cabinet. All participant data will be anonymised by allocating each participant with an ID number. Anonymised participant data will be saved on a password-protected secure computer drive which only members of the research team will have access to. Participant personal identifiable data will be stored in a separate location to anonymised participant data. All data will be maintained by the Research Co-ordinator. All consent forms will be filed in a locked cabinet that only the

research team will have access to. Data inputed into the computer system will first be wiped of any identifying markers such as names/initials of each child to ensure confidentiality. Personal data will be stored for less than three months after the study and we will store research data generated by the study for 10 years. Electronic data will be stored in a secure drive that only the research team has access to.

6.2 Research governance and the conduct of the trial

The trial will be conducted to protect the human rights and dignity of the participant as reflected in the 1996 version of the Helsinki Declaration. Patients will not receive any financial inducement to participate. In order to protect the trial participants we will following will apply:

- the trial has been designed to minimise pain, discomfort and fear
- the trial has been designed to minimise any foreseeable risk in relation to the treatments involved
- the explicit wishes of the participants will be respected including the right to withdraw from the trial at any time,
- the interest of the patient will prevail over those of science and society,
- provision will be made for indemnity by the investigator and sponsor,
- contact details for further information will be provided.

We will seek ethical approval through the NHS Research Ethics Committee guidance. No new pharmaceutical compounds are used in this trial and Clinical Trials Authorisation is not required.

The Trial Manager will inform the Chief Investigator (CI) and 2 members of the Trial Management Group (TMG) who will jointly decide if the event should be reported to the main REC as an SAE. Related and unexpected SAEs will be reported to the main REC within 15 days of the CI becoming aware of the event. A SAE Form will be completed and a copy stored in the participant's records. The occurrence of adverse events during the trial will be monitored by an independent Data Monitoring Ethics Committee (DMEC) and the Trial Steering Committee (TSC). The DMEC/TSC will immediately see all SAEs thought to be treatment related and they will see SAEs not thought to be treatment related by the Trial Management Group at the next scheduled meeting.

The study will be stopped prematurely if:

1. Funding source stopped prematurely (and unable to replace it)

2. As stated, any reported Serious Adverse Events or Suspected Unexpected Serious Adverse Reaction or serious breach of the protocol will be urgently discussed with the data monitoring group and the Trial Steering Group and/or the Sponsor. Where the study was deemed to be a risk to any participant or needs to be altered by means of an amendment to the protocol (e.g. exclusion criteria) the study will be halted.

6.5 Indemnity

Normal NHS Indemnity procedures will apply.

6.6 Funding

Research funding has been secured from the National Institute of Health Research – Health Technology Assessment programme (reference: 09/169/07).

6.7 Trial Steering Committee (TSC)

A TSC will be set up and will include an independent chair and at least two other independent members, along with the lead investigator and the other study collaborators.

ASSSIST Trial Protocol Version 4.1 17/06/11

Two service users will join the steering group for collaboration on monitoring study progress. They will also be consulted on methods of dissemination of study findings for service users. They will meet at least annually (See Appendix 2 for details).

6.8 Data Monitoring and Ethics Committee (DMEC)

A DMEC committee will be set up and will comprise of an independent statistician and clinician (primary care physician and mental health professional). The role of the DMEC is to immediately see all SAEs thought to be treatment related and unexpected; they will also review outcome data. They will meet at least annually. (See Appendix 2 for details).

6.9 Recruiting centres

One centre (York) will be co-ordinating the recruitment of participants to the study

6.10 Day to day management of the trial

The chief investigator ([name]) will be in charge of the overall management of the trial. The York-based trial manager (TBA) will be responsible for the co-ordination of the study between sites. A trial coordinator and trial secretary will carry out the day to day activities involved in running the trial. Delivery of training on social stories will be carried out by a team of clinicians. A research fellow will be responsible for the qualitative components of the study.

